## 8.7 Efficacy Subgroup Analyses

The following subgroup analyses will be conducted for the primary efficacy endpoint in the ITT1 population. Treatment difference between upadacitinib treatment group and placebo group with point estimate and 95% confidence interval using normal approximation will be presented. The NRI-C approach will be used for missing data handling. No p-value will be provided for subgroup analysis.

- Sex (male, female)
- Age ( $\leq$  median, > median)

- Race (white, non-white)
- Bio-IR status (Bio-IR, non-Bio-IR)
- Baseline corticosteroid use (yes, no)
- Baseline Adapted Mayo score ( $\leq 7, \geq 7$ )
- Baseline Full Mayo score ( $\leq 9, > 9$ )
- Prior exposure to anti-TNF (yes, no) for non-Bio-IR
- Prior exposure to biologic therapy (yes, no) for non-Bio-IR
- Baseline weight ( $\leq$  median, > median)
- Presence of pancolitis at Baseline (yes, no)
- Disease duration at Baseline (≤ median, > median)
- Baseline hs-CRP ( $\leq 5 \text{ mg/L}$  and  $\geq 5 \text{ mg/L}$ )
- Region (US versus non-US)

In addition, the following key secondary efficacy endpoints will be analyzed in the Bio-IR and non-Bio-IR subgroups in the ITT1 population.

[figure not shown]
- Endoscopic remission at Week 8
- Endoscopic improvement at Week 8
- Clinical response per adapted Mayo score at Week 8

## 9.0 Safety Analyses

#### 9.1 General Considerations

Safety analyses will be performed on the safety populations in the 8-week DB induction period (Part 1, SA1 population) and the 8-week OL extended treatment period (Part 2, SA2 population). In addition, safety summaries will be provided on the all upadacitinib treated safety population (SA-UPA).

The standard safety analyses will include reporting of adverse events (AEs), adverse events of special interest (AESIs), laboratory, and vital signs measurements. Frequency tables and exposure adjusted event rate per 100 patient-years tables of subjects with

treatment-emergent adverse events (TEAEs) by system organ class (SOC) and by preferred term (PT) as in the Medical Dictionary for Regulatory Activities (MedDRA) dictionary will be provided by treatment group. All continuous laboratory parameters and vital signs variables at each visit will also be summarized by treatment group. Frequency tables of subjects meeting criteria for potentially clinically important vital sign values and for potentially clinically important laboratory values will be provided by treatment group.

The Baseline for safety analysis will be treatment dependent. For SA1 population, laboratory and vital signs measurements, the Baseline value is defined as the last available measurement before study drug administration for each subject. For SA2 and SA-UPA populations, the Baseline value is defined as the last available measurement before first dose of upadacitinib.

Missing safety data will not be imputed.

[figure not shown]
#### 9.2 Adverse Events

Adverse events (AEs) will be summarized and presented using primary MedDRA System Organ Classes (SOCs) and preferred terms (PTs) according to the version of the MedDRA coding dictionary used for the study at the time of database lock. The actual version of the MedDRA coding dictionary used will be noted in the AE tables and in the clinical study report. Specific adverse events will be counted once for each subject for calculating percentages, unless stated otherwise. In addition, if the same adverse event occurs multiple times within a subject, the highest severity and level of relationship to investigational product will be reported.

#### 9.2.1 Treatment-Emergent Adverse Events

The Treatment-Emergent Adverse Events (TEAEs) for SA1, SA2 and the SA-UPA populations are defined as follows.

Part 1 (SA1 population): TEAEs for Part 1 are defined as events that begin either on or after the first dose of the study drug in Part 1 and

- until first dose of study drug in Part 2 if the subject is enrolled into Part 2 or
- until first dose of study drug in the Maintenance Study if the subject is enrolled into the Maintenance Study or
- within 30 days after the last dose administration of the study drug for subjects who are not enrolled in Part 2 and do not participate in the Maintenance Study.

Part 2 (SA2 population): TEAEs for Part 2 are defined as events that begin either on or after the first dose of OL upadacitinib study drug in Part 2 and

- until first dose of study drug in the Maintenance Study if the subject is enrolled into the Maintenance Study or
- within 30 days after the last dose administration of the study drug for subjects who do not participate in the Maintenance Study.

**SA-UPA population:** TEAEs are defined as events that begin either on or after the first dose of upadacitinib study drug in either Part 1 or Part 2 and

- until first dose of study drug in the Maintenance Study if the subject is enrolled into the Maintenance Study or
- within 30 days after the last dose administration of the study drug in Part 1 for subjects who are not enrolled in Part 2 and do not participate in the Maintenance Study or
- within 30 days after the last dose of the study drug in Part 2 for subjects who are enrolled in Part 2 and do not participate in the Maintenance Study.

If an incomplete onset date was collected for an adverse event, the event will be assumed to be treatment-emergent unless there is other evidence that confirms that the event was not treatment-emergent (e.g., the event end date was prior to the study drug start date). The number and percentage of subjects experiencing treatment-emergent AEs will be summarized.

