During COVID-19 pandemic, investigators should make the best effort to perform the endoscopies required per protocol. For subjects with missing endoscopy at Week 8/16 when endoscopies cannot be performed due to the COVID-19 pandemic, the site should assess the status of clinical response defined by the Partial Adapted Mayo Score. If the subject is a clinical responder at Week 8/16, the subject may enter Study M14-533 Cohort 1. If the subject is a clinical non-responder at Week 8, the subject may enter Part 2. If the subject is a clinical non-responder at Week 16 the subject will discontinue from the study. A notification should be sent to the TAMD as to the responder status and which part of the program the subject will be going to prior to the transfer taking place.

The blind from Part 1 will be maintained as these subjects will be assessed simply as non-responders and moved to Part 2 for further treatment in the study. All eligible subjects entering Part 2 will receive open-label treatment with upadacitinib 45 mg QD for 8 additional weeks (until Week 16).

[figure not shown]
Subjects who achieve clinical response defined by Adapted Mayo Score at Week 8 or Week 16 and do not meet any study discontinuation criteria will be eligible to enroll into Study M14-234 Substudy 3 following written informed consent. They do not need to meet the listed inclusion and exclusion criteria in the Study M14-234 protocol prior to this transfer to Substudy 3. Subjects with missing Week 8 or/and Week 16 endoscopy during the period of COVID-19 pandemic will not be eligible to enter Study M14-234 Substudy 3. Subjects who do not achieve clinical response at Week 16 will be discontinued from the study and will not be eligible to enroll in Study M14-234. Subjects who are discontinued will complete the 30-Day Follow-up Visit as noted in [Appendix D](#).

The data collected from subjects in Part 2 will not be part of the primary efficacy analysis for the induction study; descriptive statistics will be used, and the results will be reported separately in the clinical study report.

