- b. The Baseline Visit date will serve as the reference for all subsequent visits. A \pm 3-day window is permitted around all study visits. Where COVID-19 affects an onsite scheduled Visit a \pm 7-day window is permitted for all visits after the Baseline visit.
- c. At Week 8 of Part 1, if a subject is a clinical non-responder, Week 8 will be used as the Baseline Visit for Part 2 (Extended Treatment Period).
- d. Visits for dispensing new study drug in case of temperature excursion, loss or damage or visits to retest a lab are not considered an Un-scheduled Visit. Un-scheduled visits according to this table are for purposes when the subject is coming in for a visit for evaluation and assessment.

- e. Subjects will be contacted 30 days following study drug discontinuation for an assessment of any new or ongoing AEs, except those subjects who will continue on to Substudy 3 of Study M14-234, this will not be required until the subject completes the UC program. The home pregnancy test results will be reported at this visit, as applicable, and if a pregnancy is identified, the pregnancy must be reported to AbbVie as outlined in Section 6.1.6. The 30 day follow up visit should not take place sooner than 30 days after the last dose of study drug, the allowable visit window is dependent upon what phase of the study the subject was at when discontinuing study drug. During Part 1 and 2 of the induction period a + 3 day window (30 to 33 days after last study drug date) is allowed.
- f. Update inclusion/exclusion, medical/surgical history information, and prior and concomitant therapy to assure subject eligibility.
- g. In Part 1, Physical examinations performed at Screening, Baseline, Week 8/PD and Part 2 at Week 16/PD Visits are full physical examinations which must include an assessment of extra-intestinal manifestations (EIMs). Physical exams at all other visits are symptom-based as necessary. Assessment of EIMs are required at every visit. For subjects 16 or 17 years of age a Tanner Stage check is to be completed during the physical examination at the screening visit, this may be completed by the investigator or by self-assessment (completed by the subject/legally authorized representative) per local requirements.
- h. Height (with shoes off) will be measured at Screening only for subjects \geq 18 years of age. For Subjects 16 or 17 years of age, where locally permitted, height (with shoes off) will be measured at screening, Week 8 and Week 16.

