#### The study consists of:

[figure not shown]
- 1. Screening period of up to a maximum of 35 days;
- 2. **Part 1:** a randomized, placebo-controlled 8-week double-blind (DB) induction period;
- 3. **Part 2:** an 8-week open-label (OL) extended treatment period for subjects who do not achieve clinical response at Week 8 of Part 1;
- 4. 30-day follow-up period.

The schematics of the study design are shown in Figure 1.

Figure 1. Study Schematic

UPA = Upadacitinib
DB = double blind
QD = once daily
OL = open-label

In Part 1, approximately 462 subjects will be enrolled. Eligible subjects will be randomized in a 2:1 ratio to one of the two treatment groups (DB upadacitinib 45 mg QD or matching placebo) for 8 weeks.

- Group 1: Upadacitinib 45 mg QD (blinded, n = 308)
- Group 2: Placebo QD (blinded, n = 154)

[figure not shown]
Part 2 is an 8-week OL extended treatment period for subjects who did not achieve clinical response at Week 8 in Part 1. The objectives of Part 2 are to offer upadacitinib induction treatment to placebo clinical non-responders from Part 1, and to evaluate delayed clinical response to upadacitinib in subjects who do not initially respond to upadacitinib during Part 1.

Subjects who achieve clinical response at Week 8 (Part 1) or Week 16 (Part 2) will be eligible to enroll into Study M14-234 Substudy 3 (denoted by Maintenance Study thereafter) following written informed consent. Subjects who do not achieve clinical response at Week 16 will be discontinued from the study and will not be eligible to enroll into the Maintenance Study. Subjects who discontinued will complete the 30-Day follow-up visit.

The data collected from subjects in Part 2 will be exploratory in nature and will not be part of the primary efficacy analysis for the study; only descriptive statistics will be provided for Part 2.

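### SAP 9.2.1 has no stop for entry to Study M14-533, so for responders who roll over after a COVID-missed endoscopy, events starting on next-study treatment could be counted as M14-675 TEAEs

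*SAP*

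**What the plan says.** SAP 2.2 says that responders will be "eligible to enroll into Study M14-234 Substudy 3 (denoted by Maintenance Study thereafter"), so the defined term covers that one study. The SAP does not mention M14-533.

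SAP 9.2.1 defines TEAE windows for SA1, SA2 and SA-UPA. Each has a stop at the next study: "until first dose of study drug in the Maintenance Study if the subject is enrolled into the Maintenance Study". SA1 also stops at the first Part 2 dose. Everyone else gets 30 days after last dose. In Part 1 that bullet is "for subjects who are not enrolled in Part 2 and do not participate in the Maintenance Study"; in Part 2 it reads "within 30 days after the last dose administration of the study drug for subjects who do not participate in the Maintenance Study". SA-UPA repeats both forms.

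Protocol 5.1 adds a route for subjects whose Week 8 or Week 16 endoscopy could not be done because of the pandemic. Response is then judged on the Partial Adapted Mayo score, and "If the subject is a clinical responder at Week 8/16, the subject may enter Study M14-533 Cohort 1". The same section says "Subjects with missing Week 8 or/and Week 16 endoscopy during the period of COVID-19 pandemic will not be eligible to enter Study M14-234 Substudy 3".

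On follow-up, protocol 6.1.4 collects adverse events until 30 days after study drug stops. Appendix C, footnote e, requires the 30-day contact of all subjects "except those subjects who will continue on to Substudy 3 of Study M14-234". The Follow-Up Period text in 5.3.1.1 makes the same single exception.

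**The concern.** The SAP's own principle is that once a subject starts treatment in the next period, new events belong to that period. It applies this to Part 2 and to Substudy 3. A subject who moves to M14-533 also goes on to a further study but loses the stop, and no reason is given. It looks like an oversight: the SAP was revised for COVID-related missing efficacy data, but the TEAE windows were not revised for the COVID-related roll-over route.

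Three things follow if such events reach the M14-675 data:

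- In SA1, an event starting on M14-533 treatment would be charged to the subject's Part 1 arm, placebo included. It would enter the adverse-event overview, for which SAP 9.2.2 plans between-arm differences with 95% confidence intervals, and the counts of events of special interest, where a single event can matter.
- Roll-overs to the two studies would be handled differently for no stated reason.
- SAP 9.2.4 counts only study drug exposure in patient-years, so the extra events add to the numerator and nothing to the denominator.

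**Working it through.** **Which rule applies.** Take a Part 1 responder with a COVID-missed Week 8 endoscopy who enters M14-533.

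1. Part 2 stop: not applicable, because Part 2 is for non-responders.
2. Maintenance Study stop: not applicable, because protocol 5.1 bars this subject from Substudy 3.
3. The subject is therefore in neither Part 2 nor the Maintenance Study, and the 30-day bullet applies.

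The same reasoning holds at Week 16 for SA2, and for SA-UPA. The protocol does not close the gap: its TEAE text (8.1.8.2.1) has only the 30-day limit.

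**Length of the overlap.** With last dose on day D, the default window runs from D+1 to D+30. If M14-533 dosing starts on D+g, the overlap is max(0, 31 − g) days.

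| g | Overlap (days) |
|---|---|
| 1 | 30 |
| 4 | 27 |
| 8 | 23 |
| 15 | 16 |
| 31 or more | 0 |

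Neither document gives g. The maximum, 30 days, is 30/56 = 54% of a nominal 56-day part, per affected subject. With a stop at first M14-533 dose the overlap is 0 for every g.

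**How many Part 1 subjects could be affected.** The documents give no count, so this is an estimate.

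- SAP Appendix D dates the first and last randomizations 24 October 2018 and 26 May 2020, which is 581 days inclusive.
- The last nominal Week 8 is 26 May 2020 + 56 days = 21 July 2020.
- The itemized changes for Amendment 4 do not list the M14-533 text as new, so it probably came in with Amendment 3 of 29 April 2020. A Week 8 visit on that date means randomization on 4 March 2020.
- 4 March to 26 May 2020 is 84 days inclusive, and 84/581 = 14.5%.
- Assuming uniform accrual: 462 × 0.145 ≈ 67 subjects, about 22 placebo (154 × 0.145) and 45 upadacitinib (308 × 0.145).

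Further assumptions: 2% to 10% of these miss the Week 8 endoscopy, and 35% of placebo and 70% of upadacitinib subjects respond.

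- Placebo: 22.3 × 0.02 × 0.35 = 0.2, up to 22.3 × 0.10 × 0.35 = 0.8.
- Upadacitinib: 44.5 × 0.02 × 0.70 = 0.6, up to 44.5 × 0.10 × 0.70 = 3.1.

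**Effect on rates.** If a fraction f of an arm rolls over, the full 30 days count, and the event rate in the tail is unchanged, the rate per 100 patient-years is overstated by f × 30/56. At the upper ends above:

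- Placebo: f = 0.8/154 = 0.5%, overstatement about 0.3%.
- Upadacitinib: f = 3.1/308 = 1.0%, overstatement about 0.5%.

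Week 16 roll-overs from Part 2 are not estimated here.

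**The case against.** The strongest reply is that the harm depends on facts outside these documents. They do not say whether an event starting after the first M14-533 dose is recorded in M14-675, in M14-533 or in both. Footnote e shows only that the 30-day contact is not waived; it does not prove that the events reach this database. The documents do not describe Cohort 1 treatment or when its dosing starts. All of that stands, and it is why the point is conditional.

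A reader might infer that next-study events are in fact counted, or that the placebo arm is contaminated by events on active drug. The documents support neither. They call M14-533 a long-term extension but do not say what a placebo responder receives there.

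A reader might also apply the assumed rates to all randomized subjects: 154 × (0.02 to 0.10) × 0.35 = 1 to 5 placebo, and 308 × (0.02 to 0.10) × 0.70 = 4 to 22 upadacitinib. That ignores calendar time, because most Week 8 visits came before the probable start of the route. Its upper end implies 46 missed endoscopies (10% of 462), or 46/67 = 69% of the exposed subjects. That is implausible when protocol 5.1 asks for best efforts and 5.3.1.1 allows a wider window and other facilities.

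Finally, a 30-day tail is the SAP's ordinary rule for subjects who leave treatment, so tail days are not an anomaly in themselves. True, but those subjects are not expected to be on treatment in a following study. What does not fall to any of this is the text: the rule as written assigns these subjects the wrong kind of window, and AE collection under M14-675 remains open for them.

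**Conclusion.** The gap is real and the consequence is conditional. As written, SAP 9.2.1 would count up to 30 days of events arising after first M14-533 dose in SA1, SA2 and SA-UPA, if those events are recorded in M14-675. This contradicts the SAP's handling of the other roll-overs.

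The size is probably small: around one placebo subject or fewer and about three upadacitinib subjects or fewer in Part 1, with rate inflation of about half a percent or less. That rests on uniform accrual, a route start of 29 April 2020, 2% to 10% missed endoscopies and 35% and 70% response, all assumed. Rates in the tail could differ from those on study drug.

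The between-arm concern is limited to SA1, because all Part 2 subjects receive open-label upadacitinib. No efficacy endpoint, alpha or power figure is involved. The case for changing it rests on possible misattribution to an arm and on consistency, rather than on a large expected bias.

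**What to change.** In SAP 9.2.1, for SA1, SA2 and SA-UPA, add *or Study M14-533* after the Maintenance Study in the stopping bullets and in the exclusions within the 30-day bullets. The window then ends at first dose in whichever study follows.

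Reconcile the 30-day follow-up exception in protocol 5.3.1.1 and Appendix C, footnote e, with that definition, since both now name only Substudy 3 entrants, and state in which study's data an event after the first M14-533 dose is recorded.

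The cost is a few words in the SAP and a clarification in the protocol. The only extra data item is the first M14-533 dose date. There is no statistical downside.

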#### 9.2.2 Adverse Event Overview

[figure not shown]
An overview of AEs will be presented consisting of the number and percentage of subjects experiencing at least one event for each of the following AE categories:

- Any TEAE
- Any TEAE related to study drug according to the investigator
- Any severe TEAE
- Any serious TEAE
- Any TEAE leading to discontinuation of study drug
- Any TEAE leading to death
- TEAEs of Special Interest (as defined in Appendix B)
- All deaths
  - $\circ$  Deaths occurring  $\leq 30$  days after last dose of study drug
  - O Deaths occurring > 30 days after last dose of study drug

In addition, an overview of AEs per 100 patient-years of study exposure will be presented for the AE categories defined above. The number of TEAEs reported, the total number of years of study drug exposure, and the TEAE rate per 100 patient-years will be presented. For the SA1 population, 95% CI will be provided for the treatment differences between upadacitinib 45 mg QD and placebo.

## 9.2.3 Treatment-Emergent Adverse Events by SOC and/or PT

Treatment-emergent adverse events will be summarized by SOC and PT; by maximum relationship to study drug as assessed by the investigator (e.g., reasonable possibility or no reasonable possibility) and SOC and PT; by maximum severity and SOC and PT; and by subject number and SOC and PT. Specific adverse events will be counted once for each subject for calculating percentages, unless stated otherwise. In addition, if the same adverse event occurs multiple times within a subject, the highest severity and level of relationship to investigational product will be reported. The SOCs will be presented in alphabetical order, and the PTs will be presented in alphabetical order within each SOC.

For summary by maximum severity, if a subject has an AE with an unknown severity, then the subject will be counted in the severity category of unknown, even if the subject has another occurrence of the same event with a severity present. The only exception is if the subject has another occurrence of the same AE with the most extreme severity – severe. In this case, the subject will be counted under the severe category.

For summary by maximum relationship to study drug, if a subject has an AE with an unknown relationship, then the subject will be counted in the relationship category of "unknown," even if the subject has another occurrence of the same event with a relationship present. The only exception is if the subject has another occurrence of the same AE with a relationship assessment of "Reasonable Possibility." In this case, the subject will be counted under the "Reasonable Possibility" category.

[figure not shown]
In addition, treatment-emergent adverse events will be summarized by PT and sorted by decreasing frequency for the upadacitinib 45 mg QD treatment group.

## 9.2.4 Treatment-Emergent Adverse Events per Patient-Years of Exposure

Exposure-adjusted AEs per 100 patient-years will be provided, where AEs per 100 patient-years of exposure are defined as the number of AEs divided by the total exposure in 100 patient-years, i.e.,

where total patient years is defined as the sum of the study drug exposure of all subjects, normalized by 365.25, and rounded to 1 decimal place. Note that one event per preferred term per day per subject will be counted in the calculation of the number of AEs (i.e., a preferred term will not be counted twice on the same day for the same subject).

The TEAE rates per 100 patient-years of exposure will be provided for each AE category in the AE overview summary (defined in Section 9.2.2) and for TEAE summary by SOC and PT.

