6.1.4 Adverse Event Collection Period

All adverse events reported from the time of study drug administration until 30 days following discontinuation of study drug administration have elapsed will be collected, whether solicited or spontaneously reported by the subject. In addition, serious adverse events and protocol-related nonserious adverse events will be collected from the time the subject signed the study-specific informed consent.

Adverse event information will be collected as shown in [Figure 3](#).

Figure 3. Adverse Event Collection

Additionally, in order to assist the adjudication process, additional information on any potential MACE will be collected, if applicable.

In case of any of the following reported events, an appropriate supplemental cardiovascular events eCRF should be completed:

- Cardiac events;
- Myocardial infarction or unstable angina;
- Heart failure;
- Cerebral vascular accident and transient ischemic attack.

In case of a reported AE of herpes zoster, or a non-cardiac, non-CNS embolic or thrombotic event, the respective Supplemental AE eCRF should be completed.

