8.1.5.2 Study Drug Exposure

Exposure to study drug will be summarized for all subjects who have received at least one dose of study drug for each part and over the entire study. The duration (days) of study drug treatment will be summarized with the mean, standard deviation, median and range for each treatment group. The duration of treatment is defined as the difference between the dates of the first and last doses of the treatment plus 1 day. Study drug compliance will be summarized for each treatment group. Compliance is defined as the number of tablets taken (i.e., the difference between the number of tablets dispensed and the number of tablets returned) divided by the number of tablets a subject is supposed to take each day times the length of time that the subject was in the Treatment Phase of the study (i.e., Final/Discontinuation Visit date during Treatment Phase – Day 1 [Baseline] Visit date + 1). Subjects with missing data for the number of tablets returned will be excluded from the summary.

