## 6.0 Study Drug Duration and Compliance

For the safety populations (SA1 and SA2), duration of treatment will be summarized for each treatment group. Duration of treatment is defined for each subject as last dose date minus first dose date + 1. Duration of treatment will be summarized using the number of subjects treated, mean, standard deviation, median, minimum and maximum. In addition, the number and percentage of subjects in each treatment duration interval ( $\ge 2$  weeks,  $\ge 4$  weeks,  $\ge 6$  weeks,  $\ge 8$  weeks) will be summarized.

Treatment compliance will be summarized for each treatment period by treatment group. Treatment compliance is defined as the number of tablets actually taken divided by the number of tablets that should have been taken. Percent compliance will be summarized.

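### SAP rates per 100 patient-years count adverse events up to 30 days after the last dose but divide by time on drug only: a minor point, mainly for SA2 and SA-UPA

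*SAP*

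**What the plan says.** **Numerator.** SAP 9.2.1 ends the TEAE window at the first dose of the next part or of the Maintenance Study for subjects who continue. For the others it adds a 30-day tail. For SA1 subjects who enter neither Part 2 nor the Maintenance Study, the rule begins "within 30 days after the last dose administration of the study drug for subjects who are not enrolled in Part 2 and do not participate". A matching rule applies to SA2. SA-UPA has one bullet for each part; the bullet for those who took Part 2 drug and stayed out of the Maintenance Study begins "within 30 days after the last dose of the study drug in Part 2 for subjects who are enrolled in Part 2".

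Events in the tail are actively sought. Under protocol 6.1.4, all adverse events "until 30 days following discontinuation of study drug administration have elapsed will be collected". Protocol Appendix C, note e, adds: "Subjects will be contacted 30 days following study drug discontinuation for an assessment of any new or ongoing AEs".

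**Denominator.** SAP 9.2.4 divides the number of events by total patient-years, "where total patient years is defined as the sum of the study drug exposure of all subjects, normalized by 365.25". SAP 9.2.2 states that "an overview of AEs per 100 patient-years of study exposure will be presented for the AE categories defined above" and shows years of study drug exposure beside the rate. SAP 9.2.6 gives rates for adverse events of special interest (AESIs) on the same basis.

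SAP 9.2.4 does not define a subject's exposure. SAP 6.0, written for SA1 and SA2, says: "Duration of treatment is defined for each subject as last dose date minus first dose date + 1". Protocol 8.1.5.2, headed Study Drug Exposure and covering each part and the whole study, says: "The duration of treatment is defined as the difference between the dates of the first and last doses of the treatment plus 1 day". Neither document adds the tail to the denominator or restricts the rate numerator to events on drug.

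**The concern.** A rate is interpretable when events and person-time cover the same period. Here, up to 30 days per non-continuing subject add events but no person-time, so the rate is too high to the extent that events follow the last dose.

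The design decides where this bites. In Part 1, Week 8 responders may enter the Maintenance Study and non-responders may enter Part 2, so mainly early stoppers carry a tail. In Part 2, every Week 16 non-responder is discontinued (SAP 2.2) and carries one. SA2 and SA-UPA have no comparator arm, so their absolute adverse event and AESI rates are read on their own. The AESIs include serious infection, herpes zoster, malignancy, major cardiovascular events and venous thromboembolism.

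**Working it through.** The documents state no event rate, patient-year total or early-stopping share, so there is no figure to reproduce.

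**Inputs from the documents:** 56 planned days per part; a 30-day tail; 308 upadacitinib and 154 placebo subjects.

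**Assumptions:** e = share stopping early in Part 1; d = their mean days on drug; c = share completing Part 1 without continuing; s = share of Part 2 subjects who do not continue; k = event rate after the last dose divided by the on-drug rate. The tail is taken as fully observed, and the gap before the next part as negligible for those who continue. Each factor is the rate as the SAP defines it divided by the on-drug event rate.

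**One subject, k = 1.** (56 + 30)/56 = 86/56 = 1.54. With 112 days of upadacitinib over both parts: 142/112 = 1.27.

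**SA1.** Factor = 1 + 30k(e + c)/[56(1 − e) + de]. With k = 1 and d = 28:
- e = 4%, c = 0: 1 + 1.2/54.88 = 1.022
- e = 4%, c = 3%: 1 + 2.1/54.88 = 1.038
- e = 12%, c = 0: 1 + 3.6/52.64 = 1.068
- e = 12%, c = 3%: 1 + 4.5/52.64 = 1.085

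Varying d from 14 to 42 moves these only to 1.02–1.04 and 1.07–1.09.

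**SA1, between arms.** The spurious rate ratio is 1.00 at equal shares, about 1.02 at 4% vs 8% early stopping, and 1.04–1.05 at 4% vs 12%. For scale, planned on-drug time is 308 × 56/365.25 = 47.2 and 154 × 56/365.25 = 23.6 patient-years. At an assumed 300 events per 100 patient-years that is about 142 and 71 events, and Poisson error alone gives a 95% factor of exp(1.96 × √(1/142 + 1/71)) = 1.33.

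**SA2, k = 1.** Factor = 1 + 30s/56 if all complete, or 1 + 30s/53.76 if 8% stop early at a mean of 28 days (0.92 × 56 + 0.08 × 28 = 53.76), these being included in s.

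| s | all complete | 8% stop early |
|---|---|---|
| 30% | 1.161 | 1.167 |
| 45% | 1.241 | 1.251 |
| 70% | 1.375 | 1.391 |

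**SA-UPA, k = 1.** Let n2 be the number entering Part 2. Factor = 1 + 30[308(e + c) + n2·s]/[308(56(1 − e) + 28e) + 53.76·n2]. If 25% of the upadacitinib arm and 55% of placebo enter Part 2, n2 = 77 + 84.7 = 161.7. With e = 4% and c = 3%, s = 30% gives 1 + 2102/25596 = 1.082; s = 45% gives 1.111; s = 70% gives 1.158. Over entry shares from 15%/45% to 35%/70%, e = 4–12%, c = 0–3% and s = 30–70%, the range is 1.061 to 1.213.

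**Sensitivity to k.** The excess is proportional to k. At k = 0.5, SA2 is 1.080–1.195 and SA-UPA 1.030–1.106. At k = 0 there is none.

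**The one planning figure.** Protocol 5.2 expects about 210 subjects to be re-randomised into Study M14-234 Substudy 3 after responding to upadacitinib. It does not say whether this means Week 8 responders only or Week 16 responders as well. The central SA-UPA case implies 308 × (1 − 0.04 − 0.03 − 0.25) = 209 at Week 8, which fits the first reading (210/308 = 68%). Adding Part 2 continuers, 161.7 × (1 − s), gives 258 to 323, which does not fit the second. The second reading would mean fewer subjects continuing, and so larger factors. The figure therefore does not settle the shares.

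**The case against.** The strongest reply is that the denominator is a stated choice. The rates are called exposure-adjusted and given per 100 patient-years of exposure, with years of drug exposure printed alongside. No hypothesis test is touched. The mismatch can only raise the reported upadacitinib rates in SA2 and SA-UPA, so it hides no harm. Some subjects withdraw or are lost before day 30, so the tail is not always fully observed. Off-drug days may also include other treatment, which protocol 5.4.1 allows, and would dilute a rate meant to describe the drug.

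Most of this stands and is why the point is minor. It does not remove the point: the label names the denominator but does not tell the reader that the count runs up to 30 days beyond it. Dilution is a reason to report both rates. The displayed equation in SAP 9.2.4 is not legible in the text available, but the words around it define both terms.

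Two stronger readings are tempting and not supported:

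- **Late deaths.** The overview categories in SAP 9.2.2 include deaths more than 30 days after the last dose, and rates are promised for those categories. A reader might infer that deaths which cannot fall in exposure time will be divided by it. But 9.2.2 and 9.2.4 then speak of TEAE rates, so these rows may well be counts only. A note saying so is enough.
- **Study M14-533.** Protocol 5.1 lets some responders whose endoscopy was missed because of COVID-19 enter M14-533, which is not the Maintenance Study as the SAP defines it. A reader might infer that their later events would be attributed to this trial. That depends on how M14-533 records its events, which these documents do not show.

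**Conclusion.** The mismatch is in the current SAP text. It rests on one inference: that study drug exposure in 9.2.4 means the first-to-last-dose length in SAP 6.0 and protocol 8.1.5.2. No other definition exists in either document.

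The scope is narrow. Percentages of subjects are unaffected. The SA1 95% confidence interval in 9.2.2 is probably unaffected, because the version history calls it a risk difference. A reader might infer a biased safety comparison between arms; the documents do not support that, because the direction is unknown and the size is well inside sampling error.

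What remains is overstatement of supplementary descriptive rates: about 1.02–1.09 in SA1, 1.16–1.39 in SA2 at an assumed 30–70% not continuing, and 1.06–1.21 in SA-UPA. For the assumed shares these are near upper bounds, unless the event rate rises after the last dose. The per-subject 1.54 is not a study-level effect. Severity: minor, and worth correcting because the correction is cheap.

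**What to change.** In SAP 9.2.4, add a rate per 100 patient-years at risk. Each subject's person-time runs from the first dose in the analysis set to the earliest of last dose + 30 days, first dose of the next part or study, or the end of that subject's data. Report it beside the existing drug-exposure rate, label both, and use the same two terms in 9.2.2 and 9.2.6. State in 9.2.4 that exposure runs from first to last dose. In 9.2.2, note that deaths more than 30 days after the last dose are shown as counts, if that is intended, and name the measure to which the SA1 confidence interval refers.

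The cost is SAP wording, one derived person-time variable from dates already collected, and a second column of rates. The drawback is that off-drug days can dilute the on-drug rate when risk falls after the last dose; the retained drug-exposure rate lets the reader see this.
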